## Minimization of Biases by Prior Knowledge of the Intervention:

The process described also helps to minimize biases that could arise due to the expectation or advance knowledge about the application of anesthesia. Even if the patient has previously signed the informed consent, it is important to consider that a high percentage of patients do not read the entire content of the consent in detail or do not remember all the aspects mentioned, especially the part referring to anesthesia. This simulates a masking in the study, in which the patient does not know if she will be given anesthesia, which allows the perception of pain to be more objectively assessed without the expectation of treatment influencing her experience.

Even if the test has been verbally explained in the consultation, the patient may not remember all the details related to anesthesia on the day of the intervention. This approach ensures that the perception of pain in each group (with or without anesthesia) is not affected by the patient's mental or emotional predisposition to know the treatment in advance. Therefore, biases related to expectation are reduced, which improves the quality of the data obtained.

## **Patient Randomization**

## Randomization Method

For the assignment of the patient to the groups (with anesthesia or without anesthesia), a simple 1:1 randomization method will be used, which means that each patient has a 50% chance of being assigned to each group.

A completely random and reliable system will be used for patient allocation. https://www.random.org/, which allows you to generate assignments without bias.

A random number (between 1 and 100) will be assigned to each patient, and it will be established that the odd numbers correspond to the group with anesthesia (**Group A**) and the even numbers to the group without anesthesia (**Group B**). It will be noted in the Clinical Judgment.

Alternatively, a system of opaque bags with numbered papers can be used to perform randomization directly in the office, in case you prefer not to use software. (But preferably you should use the software if you can)

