## Importance of a well-designed clinical trial.

A well-designed randomized clinical trial has the ability to reduce biases and provide more robust evidence on the efficacy of interventions, such as anesthesia, in reducing pain during hysteroscopy. In this sense, the study design should include a representative sample of patients, a standardized method of pain assessment (such as the VAS scale), and strict control of confounding variables that may influence pain perception, such as the professional's experience, previous anxiety, and the type of intervention.

Through a more rigorous design, the study will also be able to identify predictors of pain and contribute to the development of evidence-based recommendations for pain management in hysteroscopy. This evidence is critical, as it not only improves the quality of the procedure, but also has the potential to optimize the patient experience, improving treatment adherence and reducing the need for general anesthesia.

In addition, variables that will give rise to new hypotheses will be included, such as the "indication of surgical hysteroscopy for pain". Knowledge of this data will allow later, according to the results obtained in the trial and after analysing the costs per procedure, to carry out new cost-effectiveness studies and assess whether anaesthesia can really be an efficient strategy in the face of non-application of anaesthesia.

For all these reasons, this study is of great relevance for the field of gynecology and ambulatory surgery, since it will specifically address the gaps in the existing literature on pain management during hysteroscopy, strengthening the quality of the evidence in this field. This is essential to improve clinical practice, offering a solid basis for decision-making in pain management in outpatient gynecological procedures.

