## Objectives of the study

The aim of the study is to demonstrate whether locoregional anaesthesia has an impact on the pain perception of patients who undergo ambulatory hysteroscopy, i.e. to demonstrate whether there are significant differences in pain perception in patients who undergo such anaesthesia and those who do not.

H0: Half pain (VAS) analgesia = half pain (VAS) without analgesia

As secondary objectives, if differences are demonstrated, we will try to show which variables interfere with the patient's pain through a logistic regression analysis.

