## **Clinically Relevant Difference:**

• In previous studies, a reduction of at least 1.3 - 1.5 points in VAS has been considered to be clinically meaningful in gynecological procedures. □ Proposal: Establish an expected difference of 1.5 points in the VAS.

**Standard deviation** of pain in hysteroscopy without anesthesia:

According to previous studies, the standard deviation of pain ranges from 1.8 to 2.5 points in VAS.

Proposal: Use a standard deviation ( $\sigma$ ) of 2.0 for the calculation.

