## Level of significance:

It is set at 5% (0.05), which implies a probability of type I error of 5% (rejecting the null hypothesis when it is true).

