## **Statistical power:**

The statistical power is set at 80% (0.8), which implies a 20% probability of type II error (not detecting a real difference).

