#### **Final Estimate**

To calculate the sample size in a clinical trial comparing pain in two groups (with and without anesthesia), we used the formula to compare two independent means. The effect size (Cohen's d) is obtained by dividing the clinically relevant difference by the standard deviation, obtaining a moderate-high effect size according to Cohen's classification.

Using a t-test for two independent samples, the sample size that provides the desired power is sought. When the information is entered into sample size calculation software, the result is a sample size of 29 patients per group. This means that the study will need a total of **58** patients.

If follow-up losses are anticipated, it is recommended to increase the sample size by 10-20%. Therefore, it would be advisable to include between **64 and 70 patients** in total to ensure adequate statistical power.

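### Simple randomisation does not ensure equal arms or balance in key pain predictors in a trial of 58 to 70, and the stated primary test adjusts for none of them

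*Protocol*

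**What the plan says.** Under Randomization Method the protocol states that "a simple 1:1 randomization method will be used, which means that each patient has a 50% chance of being assigned to each group". A random number from 1 to 100 is drawn for each patient; odd means anaesthesia and even means none. The Summary of the Consent Delivery Procedure also specifies simple 1:1 randomisation. No blocks, strata or minimisation are mentioned. Numbered papers in opaque bags are allowed as an alternative, without saying whether a drawn paper is replaced.

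Under Final Estimate, "the result is a sample size of 29 patients per group", that is 58 in total, with 64 to 70 advised to cover losses. Under Sample size calculation the primary VAS comparison is a Student's t-test, or Mann-Whitney U if the data are not normal, with no covariate.

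The section on the importance of a well-designed trial says that the design should include "strict control of confounding variables that may influence pain perception", and gives operator experience, prior anxiety and type of intervention as examples. Predictors are recorded, compared descriptively and explored in subgroups. A regression appears only under Objectives, as a secondary step conditional on a difference being shown.

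**The concern.** The sample size is expressed as a number per group and the background asks for close control of pain predictors, but neither the allocation nor the named primary test acts on either. In a trial this small, one arm can by chance hold noticeably more nulliparous or postmenopausal women. With no adjustment in the primary comparison, a reader of the baseline table cannot tell how far such a split moved the VAS difference. A descriptive table shows an imbalance but does not correct it. What is at stake is some precision, and the credibility of a single small unblinded trial with a subjective endpoint.

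**Working it through.** **Inputs from the protocol.** Alpha: "It is set at 5% (0.05". Power: "The statistical power is set at 80% (0.8". Difference: "Establish an expected difference of 1.5 points in the VAS". Standard deviation: "of 2.0 for the calculation". Sidedness is not stated; it is taken as two-sided because the aim is to "demonstrate whether there are significant differences in pain perception" and the null hypothesis is equality of means. Standardised difference d = 1.5/2.0 = 0.75.

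**1. The plan's own figure.** The noncentral t solution is n = 28.9, so 29 per group. Power is 78.7% at 28/28 and 80.1% at 29/29. The protocol's 29 is reproduced.

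**2. Arm sizes.** Of the numbers 1 to 100, 50 are odd, so the size of one arm is Binomial(N, 0.5).

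| N randomised | P(exactly equal) | P(both arms at least 29) | P(arms differ by 10 or more) | 95% range of one arm |
|---|---|---|---|---|
| 58 | 10.4% | 10.4% | 24% | 22 to 36 |
| 64 | 9.9% | 62% | 26% | 24 to 40 |
| 70 | 9.5% | 88% | 28% | 27 to 43 |

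These are counts as randomised, before any losses.

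**3. Effect on power.** For arms n1 and n2 the noncentrality is d·√(n1·n2/(n1+n2)).
- 29/29: 0.75 × √(841/58) = 2.856, power 80.1%.
- 25/33: power 79.4%.
- 22/36: 0.75 × √(792/58) = 2.771, power 77.8%.
- Averaged over the binomial split at N = 58: 79.4%, a loss of 80.1 − 79.4 = 0.7 points.
- With all patients analysed, the average is 83.4% at N = 64 and 86.7% at N = 70.

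**4. Balance of one binary predictor.** The protocol gives no prevalence, so 20% to 50% is assumed. Probability that the two arms differ by 20 percentage points or more under simple randomisation:

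| Assumed prevalence | N = 58 | N = 70 |
|---|---|---|
| 20% | 6% | 4% |
| 30% | 10% | 7% |
| 50% | 14% | 10% |

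For five independent predictors at 30% prevalence and N = 58, the chance that at least one differs this much is 1 − (1 − 0.099)^5 = 41%. Independence is also an assumption.

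**5. What each remedy does.**
- Equal arms alone do not help balance. At 30% prevalence and N = 58, a 20-point difference occurs in 11% of trials with fixed 29/29, against 10% with simple randomisation.
- Blocks of 4 and 6 stratified on the factor itself gave no 20-point difference in that factor in 20,000 simulated trials at 50% prevalence; the smaller arm averaged 28.5. An unfinished block of 6 leaves the arms at most 3 apart, so two strata leave them at most 3 + 3 = 6 apart (26/32 at N = 58, power 79.7%).
- If the factor explains a share R² of VAS variance, adjustment changes d to 0.75/√(1 − R²) and costs one degree of freedom. At 29/29, power is 82% for R² = 5%, 84% for 10% and 88% for 20%. These shares are assumptions.

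**The case against.** Several points on the other side stand.

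- A reader might infer that simple randomisation cannot deliver the planned group sizes. The documents do not support that. The figure of 29 is the output of a calculation, not a promise of exact arms, and with the advised 64 to 70 both arms reach 29 as randomised in 62% to 88% of trials.
- A reader might also infer that the method biases the result. It does not: chance imbalance neither biases the estimate on average nor inflates type I error, and the standard error of the unadjusted test already reflects it.
- For any single predictor a large imbalance is uncommon. It becomes likely only at a lower threshold or across many predictors.
- The sentence on controlling confounders is background and promises no balanced allocation. The protocol also relies on eligibility limits, a standardised procedure and recording of covariates, and it admits that external variables cannot all be held constant.
- Blocking has a real cost here. The operator knows the allocation and the group is written in the clinical record, so past allocations are visible and some later ones could be guessed. Unrestricted draws avoid this.
- A separate analysis plan, not shown, may add covariate adjustment, and the unadjusted test is named within the sample-size section.

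What remains is that the allocation method is fixed in this protocol and cannot be changed at the analysis stage, and that the only primary test the protocol names uses no predictor.

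**Conclusion.** The point holds as a minor one. Unrestricted allocation with an unadjusted primary test leaves arm sizes and predictor balance to chance. The price is under 1 point of power on average, plus about a 6% to 14% chance per binary predictor of a 20-point imbalance at 58 patients (4% to 10% at 70). The larger gain comes from adjustment: from 80.1% to about 82% to 88% power at 29/29. These sizes rest on a two-sided test, d = 0.75, prevalences of 20% to 50% and a factor explaining 5% to 20% of VAS variance; the last two are not in the protocol.

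Two limits apply to any remedy. Stratification protects only the factor used. And no allocation method guarantees 29/29 analysed, because patients are removed after randomisation under the exclusion criteria for complex procedures, the section on patients excluded from the study and the per-protocol analysis.

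**What to change.** 1. In Randomization Method and in step 3 of the Summary of the Consent Delivery Procedure, replace the per-patient draw with a list generated in advance, in randomly varying blocks (for example 4 and 6) whose sizes are not disclosed, held by someone other than the recruiting clinicians. Remove the opaque-bag alternative or bring it under the same list.
2. Stratify by one factor that is known at indication and already recorded, for example menopausal status or any previous vaginal delivery. Polyps actually treated will not serve: randomisation takes place at indication and polyps are identified during the procedure.
3. In Sample size calculation, state that the primary VAS comparison includes that factor as a covariate, for example in a linear model. If a rank test is kept as the fallback, use a form stratified by the same factor, such as the van Elteren test.

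The cost is one list made before enrolment, one person to hold it, and one degree of freedom. The downside is that some late-block allocations may be guessed in this open trial; varying, undisclosed block sizes limit this but do not remove it. If the sponsor prefers unrestricted draws for that reason, item 3 alone should still be adopted, with the covariate named before enrolment.

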#### **Selection Bias:**

If randomization is not performed strictly, inhomogeneous patient selection may occur, which would affect the validity of the results.

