## Randomization process

Randomization will be carried out at the time the patient presents for the intervention (in consultation, when the indication is made), after she has read and signed the informed consent. At this time, you will be randomly assigned to one of two groups (under or without anesthesia) using the system previously described.

The inclusion of the patient's procedure in the trial will be recorded by writing the name in the Clinical Judgment along with the group to which she belongs according to the randomization process. The patient will also be given the specific document of inclusion in the trial to sign after explaining what it consists of

and give him consent for the test. The documents will be sent for consultation according to the usual channels after filling in the surgical demand register appropriately as it is standardized in the unit.

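### Each allocation is drawn singly in the clinic by either of two optional methods, with no locked sequence, log or bar on redrawing, so an unwelcome result could be replaced without trace.

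*Protocol*

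**What the plan says.** All references are to the Protocol.

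- **Ratio.** Under Randomization Method, "a simple 1:1 randomization method will be used, which means that each patient has a 50% chance of being assigned to each group". No blocks or strata are specified.
- **Preferred source.** A public website is named, described as a tool "which allows you to generate assignments without bias". "A random number (between 1 and 100) will be assigned to each patient"; odd numbers mean anaesthesia (Group A) and even numbers mean none (Group B).
- **Alternative source.** Under the same heading, "a system of opaque bags with numbered papers can be used to perform randomization directly in the office", for users who would rather not use software. The ranking of the two is only advisory: "But preferably you should use the software if you can".
- **Moment of the draw.** Randomization process places it in the consultation where the test is indicated, after signed consent: "At this time, you will be randomly assigned to one of two groups (under or without anesthesia) using the system previously described". The group is then written in the Clinical Judgment.
- **The protocol's own warning.** Under Selection Bias: "If randomization is not performed strictly, inhomogeneous patient selection may occur, which would affect the validity of the results".

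No one is named to make the draw. The setting (consultation, office) and the statement under Data Collection that prescribing professionals refer patients to the study suggest the enrolling clinician. That is an inference.

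**The concern.** A fair number generator does not make a fair allocation procedure. The procedure is fair only if the first draw for each patient is the one used, and the protocol contains nothing that would secure this or show afterwards that it happened. A number can be generated again, a paper drawn again, or the second method tried after the first. Only the resulting group reaches the record.

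The stakes are higher here than in many trials. Possible limitations accepts that the doctor giving the anaesthetic knows the arm. The primary endpoint is a patient-reported VAS score. The section on collecting consent says that use of anaesthesia is ordinarily at the doctor's discretion, so clinicians may hold preferences for particular patients. Patient variables lists features believed to affect pain that an enrolling clinician could know, such as parity, previous dysmenorrhea and anxiety. Randomisation is the main protection left, and selection on unrecorded judgement cannot be repaired in the analysis.

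This is trial conduct, set out in the protocol's own section. A statistical analysis plan could not put it right.

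**Working it through.** **1. Is the generator fair?** Of the whole numbers 1 to 100, 50 are odd and 50 even, so one draw used once gives exactly 50/50. The claim of unbiased assignment is correct for the generator. The question is what happens between draw and record.

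**2. Does another section lock the draw?**

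| Section | What it provides | Does it lock or expose a redraw? |
|---|---|---|
| Randomization Method | Two interchangeable methods, result noted in the record | No |
| Randomization process | Draw after consent, group recorded | Fixes the order of consent and draw; only the final group is kept |
| Consent collection in hysteroscopy consultation | Group hidden from the patient | No; concerns the patient only |
| Masking of the Principal Investigator and the Statistician | Masks those two roles | No; does not cover whoever enrols |
| Document of Contingencies; Specific Commitments | Non-compliance may stop the study; investigators promise compliance | No; a redraw breaks no written rule and leaves nothing to detect |

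**3. What one redraw does to one patient.** If an unwelcome first result is redrawn once with probability r, then P(preferred arm) = 0.5 + 0.5 × r × 0.5 = 0.5 + 0.25r. This gives 52.5% at r = 0.1, 62.5% at r = 0.5 and 75% at r = 1.

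**4. Illustration of the bias.** All inputs in this step are assumed; none is in the protocol. A fraction f of recruits is expected to score d points higher. Each is redrawn once whenever first assigned to control (r = 1), so P(anaesthesia) = 0.75 for them and 0.5 for everyone else.

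- Share of such patients in the anaesthesia arm = 0.75f / [0.75f + 0.5(1 − f)]
- Share in the control arm = 0.25f / [0.25f + 0.5(1 − f)]
- Bias = d × (difference in shares)

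With f = 0.2 and d = 2: 0.15/0.55 = 27.3% and 0.05/0.45 = 11.1%. The difference is 0.162, and 0.162 × 2 = 0.32 VAS points. Against the expected difference of 1.5 under Clinically Relevant Difference, 0.32/1.5 is about 22%.

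| f | Anaesthesia arm | Control arm | Difference | d = 1 | d = 2 | d = 3 |
|---|---|---|---|---|---|---|
| 0.1 | 14.3% | 5.3% | 0.090 | 0.09 | 0.18 | 0.27 |
| 0.2 | 27.3% | 11.1% | 0.162 | 0.16 | 0.32 | 0.48 |
| 0.3 | 39.1% | 17.6% | 0.215 | 0.21 | 0.43 | 0.64 |

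**5. Direction.** Moving higher-pain patients into the anaesthesia arm raises that arm's mean and hides a benefit. If they are redrawn when first assigned to anaesthesia, the same shares apply with the arms exchanged, and a benefit is exaggerated by the same amount.

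**6. Occasional redrawing.** In a simulation with 58 patients, SD 2.0, no true effect, every patient open to steering on expected pain, and an assumed correlation of 0.3 to 0.5 between expected pain and VAS, the two-sided type I error stayed near 5% at r = 0.1. It rose to 7–12% at r = 0.5 and 15–33% at r = 1. Rare redrawing does little harm; habitual redrawing does a lot.

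**The case against.** The strongest reply is that allocation is in effect concealed. Consent comes first, and with unblocked 1:1 draws nobody can foresee the next assignment when deciding whether to enrol. This stands. A reader might infer from the missing sequence that upcoming assignments can be predicted; the protocol does not support that. What remains is replacement of a result after it is seen.

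Other points also stand in part:

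- **Who draws.** A reader might take it as stated that the recruiting clinician makes the draw. It is not stated. The gap exists whoever draws, since no independent person is assigned.
- **The bags.** They are opaque, the wording is plural and could mean one paper per bag, and software is preferred. Opacity prevents choosing a paper by sight but does not prevent a second draw, and the website route has the same gap.
- **Existing controls.** Consent before the draw, recording of the group and the compliance commitments are real, but none would reveal a redraw.
- **Group sizes.** A reader might add that simple draws do not guarantee the planned 29 per group. That does not carry weight. With the protocol's inputs (1.5 points, SD 2.0, 5% taken as two-sided), power is 80.1% at 29 + 29. Averaged over simple 1:1 splits it is 79.4% at 58 patients, 83.4% at 64 and 86.7% at 70. Across the advised 64 to 70, chance imbalance costs nothing that matters.
- **Hypothetical size.** The figures rest wholly on assumed behaviour. That is right, and they show only what the gap would permit.

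**Conclusion.** The point holds in this form: the protocol fixes a per-patient draw by either of two methods, and nothing makes the first result binding or leaves a record of discarded ones. This is the selection bias the protocol itself warns of, without a control that would prevent or reveal it. On assumed inputs the arms could differ by 0.32 VAS points (0.09 to 0.64 for 10–30% of patients and 1–3 points), in either direction according to how patients are steered. Nothing in the document shows that redrawing has occurred or is intended. A reader might also infer that the trial is biased in favour of anaesthesia; that does not follow, because the more natural motive, sparing patients expected to have more pain, would work against it. The case for change rests on the missing safeguard and the low cost of supplying it.

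**What to change.** Under Randomization Method, replace both options with one procedure:

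1. A 1:1 sequence is generated in advance by an existing staff member who neither recruits nor operates.
2. It is held in sequentially numbered, opaque, sealed envelopes.
3. After signed consent, the study ID, date and time are written on the next envelope before it is opened. Envelopes are opened strictly in order.
4. All envelopes, used and unused, are kept for audit.

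Delete the choice of method, and have Randomization process refer to this procedure. Simple randomisation may stay. Permuted blocks are optional: they even out group sizes but make assignments somewhat more predictable, and this fix does not need them.

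The cost is a short amendment, which the investigators' commitments require the ethics committee to authorise, and preparation of the envelopes (70 at the upper planned total). The practical burden is keeping one series in order across several prescribers. No extra patients or visits are needed, and the sample size does not change.
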